## **STUDY PROTOCOL.**

### **HYPOTHESIS**

Steroids form one of the pillars of immunosuppression in transplant patients. However, their use is associated with an increase in post-transplant comorbidity. Although steroid withdrawal post-transplant can improve the metabolic and cardiovascular profile in transplant patients, it is not really known whether this therapeutic strategy results in a greater risk for the de novo appearance of donor-specific antibodies (DSA), which are associated with a reduction in kidney graft survival. Also unknown is the causal relationship between the appearance of DSA and histological lesions in stable kidney transplant patients after steroid withdrawal in the third post-transplant month. Finally, another unknown is whether this immunosuppressive strategy is associated with changes in the balance between effector and suppressor lymphocyte subpopulations that selectively infiltrate the graft via peripheral homing receptors.

This randomized controlled study of stable kidney transplant patients aimed to determine the natural history after steroid withdrawal in the third month post-transplant of the de novo production of anti-HLA antibodies (DSA), by means of the sequential measurement of DSA during the first two years post-transplant. At the same time we wished to determine the repercussion of this therapeutic strategy on the kidney graft histology by performing protocol biopsies, as well as the risk factors for the appearance of de novo DSA in these patients. Finally, we aimed to monitor sequentially the balance of the lymphocyte (CXCR3highCD4+/CCR4highCD4+) and regulatory cell (Treg CCR4high) subpopulations in peripheral blood and samples of the graft tissue obtained by fine-needle aspiration puncture (FNAP) after the withdrawal of steroids versus continuation of conventional triple therapy.

The lack of prospective serological, histological and lymphocyte subset studies in kidney transplant patients in whom steroids are withdrawn makes this study very pertinent. The findings will doubtless give rise to an immunosuppressive strategy that optimizes the results of a transplant in terms of survival.

## OBJECTIVES

### *Primary objective*

To compare the incidence of de novo DSA in stable kidney transplant patients after withdrawal of steroids in the third month post-transplant as compared with patients who continue to receive conventional triple immunosuppression: steroids, tacrolimus (prolonged-release –Advagraf, or immediate-release –generic or Prograf, according to their availability in each Spanish Community) plus mycophenolate mofetil (MMF) or mycophenolic acid (MPA).

### *Secondary objectives*

1. To determine the course of the histological findings in the two treatment groups.
2. To determine the course of the balance in the subpopulations of lymphocytes (CXCR3highCD4+/CCR4highCD4+) and regulatory cells (Treg CCR4high) using flow cytometry in samples from peripheral blood and FNAP after withdrawal of steroids in the third month post-transplant versus conventional triple immunosuppression.
3. To analyze and compare the incidence of immunological dysfunction in the two treatment arms, as well as graft and patient survival at one and two years of follow-up.
4. To examine the potential metabolic and cardiovascular benefit of steroid withdrawal in terms of renal function, hypertension, diabetes and hyperlipidemia.
5. To assess the adherence to treatment with immunosuppressors in the two treatment groups and its impact on the generation of DSA.

## STUDY DESIGN AND DURATION

This was a randomized, open-label clinical trial with two treatment arms and a follow-up of two years in patients who received a first deceased-donor kidney transplant. The combinations of immunosuppressors in the study arms were those approved in the technical documentation and used routinely in clinical practice. This was therefore a phase IV clinical trial in the usual conditions of use. The patient recruitment period was 12 months. The minimum follow-up period was 24 months.

**Inclusion criteria:** a) Both male and female patients, 18 years of age or over with no immunological risk (PRA <25% and absence of DSA) who received a first deceased or living donor kidney transplant. b) Patients who for the first three months post-transplant were receiving tacrolimus plus MPA or MMF and steroids and who had stable plasma levels of tacrolimus. c) Absence of clinical or histological immune dysfunction before randomization. d) Absence of de novo DSA at the time of randomization. e) Patients who wished and were able to give their written informed consent to participate in the study. f) Female patients who agreed to use efficient contraceptive methods during the study.

**Exclusion criteria:** a) Recipients of a multiorgan transplant. b) Retransplants. c) Presence of DSA prior to transplant or at the time of randomization. d) Cold ischemia time >30 hours. e) Patients with serum creatinine levels above 2 mg/dL or proteinuria above 1g/day at the time of randomization. f) Previous episode of severe rejection (II-B-III in the Banff/09 classification) before randomization. g) Presence of subclinical rejection in the protocol biopsy before randomization. h) Patients with BK-polyomavirus nephropathy at the time of randomization. i) Patients with recurrent or de novo glomerulonephritis. j) Patients receiving treatment with immunosuppressive drugs other than those of the clinical trial in question. k) Patients who were positive against the human immunodeficiency virus (HIV) or who had a severe systemic infection and who the investigator deems the need for continued therapy. l) Patients who had had any previous malignant disease during the previous five years, except basal cell or excised squamous cell carcinoma.

**Selection procedure and coding:** Once written informed consent was obtained at the screening visit, the baseline data were collected to determine the eligibility of the patients to participate in the study. Those patients who fulfilled the inclusion criteria were randomized in a proportion 1:1 to one of the two treatment arms.

Randomization was done locally at each center via the case report form (CRF) to assign the eligible patients to one of the two treatment arms. This randomization was done using a computer program after introducing the patient data into the electronic database (CRF) and determining the

status of the anti-HLA antibodies (DSA) and the histological findings at the third month post-transplant.

**Description of the treatment groups:** After verifying the inclusion/exclusion criteria, the patients were distributed randomly in the two study groups:

**Group A:** steroids, tacrolimus (prolonged-release –Advagraf, or immediate-release tacrolimus – generic or Prograf, according to their availability in each Community) plus MMF or MPA.

**Group B:** tacrolimus (prolonged-release –Advagraf, or immediate-release tacrolimus –generic or Prograf, according to their availability in each Community) plus MMF or MPA.

**Treatment schedule:**

**Group A: Tacrolimus** 0.15 mg/Kg/day to maintain levels of 8-12 ng/ml for the first two months.

With effect from the third month tacrolimus 0.1 mg/kg/day to maintain levels of 5-8 ng/ml;

**Mycophenolate mofetil (MMF)** 2 gr/day or mycophenolic acid (MPA) 1440 mg/day for the first two weeks post-transplant. With effect from this point MMF 1-1.5 gr/day or MPA 720-900 mg/day; **Steroids:** 0.5 gr of methyl prednisolone intraoperatively and 125 mg on day 1; prednisone 30 mg for the first two weeks post-transplant, then tapering 5 mg/week to reach the dose of 5 mg/day at the second month post-transplant. After this the same dose of prednisone was continued.

This treatment was maintained throughout the whole study period in Group A.

**Group B:** These patients received the same treatment schedule as those of Group A up to the time of randomization (third month post-transplant). After this they received: **Tacrolimus** 0.1 mg/kg/day to maintain levels of 5-8 ng/ml; **MMF** 1-1.5 g/day or **MPA** 720-900 mg/day; withdrawal of steroids between the third and fourth month post-transplant as per usual practice in the center.

Both treatment groups received pre-operatively tacrolimus 0.12 mg/Kg orally and MMF 1 g. or MPA 720 mg. Both treatment groups could receive induction therapy with anti-CD25 monoclonal antibodies (Basiliximab 20 mg iv on days 0 and 4) or polyclonal antibodies (Thymoglobulin 1 mg/kg/day for 4-7 days) in patients at risk of delayed graft function and delayed introduction of tacrolimus.

**Other treatments:** Cases of acute rejection were treated with 3 boluses of 500 mg/day of i.v. methylprednisolone. Cases of steroid-resistant rejection were treated with a standard cycle of 7-10 days of rabbit thymoglobulin. Cases of acute humoral rejection were treated in accordance with the protocol at each center: plasmapheresis, immunoglobulins, and rituximab, either alone or in combination.

Drugs to treat the most usual infections, like *Pneumocystis jirovecii* or CMV, were used in accordance with the protocol at each center. Dyslipidemia was treated with statins or with ezetimibe in the event of the appearance of adverse events. Fibrates were avoided, except for gemfibrozil, as they are associated with worsening renal function. Hypertension was treated according to the protocol at each center to obtain a target BP of <130/80 mmHg. As beta blockers have been associated with new onset post-transplant diabetes, they were initially avoided unless they were indicated for another condition (ischemic heart disease, arrhythmia, or other) or in patients with refractory hypertension.

**Criteria for withdrawal of subjects from the study:** Any participant could withdraw from the study at any time, withdrawing their consent, with no need to justify their decision. The investigator could also withdraw patients from the study in the event of the appearance of any concomitant disease or adverse event that, in the judgement of the investigator, warranted withdrawing the patient from the study, or if there were violations of the protocol or other reasons. The investigator attempted to follow any patient with an adverse event at the time of withdrawal and provide the appropriate treatment in the event of any problem.

Patients who developed acute humoral or steroid-resistant rejection during the study were treated with the best maintenance immunosuppression in the opinion of the investigator and were withdrawn from the study. This could consist of adding steroids or an anti-mTOR (sirolimus or everolimus). All these patients were followed in the same way as those who remained in the protocol in order to have a more robust intention-to-treat analysis.

If the study medication was interrupted for any reason for more than 21 consecutive days or for more than two periods of 7 days or more the patient was considered to have abandoned the

treatment prematurely and was only included in the intention-to-treat analysis and excluded from the per protocol analysis.

### **Variables:**

#### *Efficacy variables:*

The *primary variable* was the presence of donor-specific anti-HLA antibodies (DSA) at 24 months.

The *secondary variables* were:

- a) Graft and patient survival.
- b) Rate of acute clinical rejection, confirmed by biopsy, calculated glomerular filtration rate (determined by aMDRD) and proteinuria at 3, 6, 12 and 24 months.
- c) BP figures and number of hypertensive patients, lipid levels and need for lipid-lowering drugs, and increase in weight and BMI.
- d) Rate of post-transplant diabetes mellitus (PTDM) or glucose intolerance one year post-transplant according to the criteria of the ADA (PTDM: baseline glycemia  $\geq 126$ , or  $\geq 200$  mg/dl after glucose overload, or need for treatment; glucose intolerance: glycemia after overload of 140-199 mg/dL).
- e) Determination of the lymphocyte subpopulations (CXCR3highCD4+; CCR4highCD4+ and Treg CCR4high) by flow cytometry at 1, 3, 6, 12, 18 and 24 months.
- f) Appearance of acute or chronic pathological lesions of the graft using:

\*Kidney graft biopsy. Biopsies were done before randomization (month 3 post-transplant) and in month 24 post-randomization (protocol biopsies). In the case of suspected acute rejection a biopsy of the graft was done before or within 48 hours of starting anti-rejection treatment. Likewise, a graft biopsy was done at any time if graft dysfunction was detected, as evidenced by proteinuria 0.5 g/day or an increase in the serum creatinine of 25% above its baseline level. The biopsies were evaluated according to the Banff'09 classification (*Sis B, et al Am J Transplant 2010;10: 464-71*). Biopsies done for clinical indication and those done prior to randomization were evaluated locally at each participating center. The local pathologist interpreted the biopsy for the presence of clinical or subclinical rejection, borderline lesions or progression of chronic lesions that

explained a possible graft failure to thus provide the most opportune treatment. The biopsies done and the pre-randomization and final visits were also sent to the pathologist at Carlos Haya Hospital, Malaga, who also interpreted and classified them using the same Banff'09 criteria. The biopsies were processed in each center and sent to the central pathologist for study. The slides comprised at least 2-3 slices of the biopsy. The staining was done locally (hematoxylin eosin, periodic acid Schiff, Masson trichrome and methenamine silver).

For the measurement of C4d an unstained slide was sent to the reference center, at ambient temperature.

\*The interpretation of the central pathologist was used mainly to analyze the progression of the chronic graft nephropathy. For each patient, the sum of the classification of the chronic lesion was obtained from the 5 histological categories: 1) cg: chronic glomerulopathy. 2) ci: chronic interstitial. 3) ct: tubular atrophy (chronic). 4) cv: arteriolar hyalinosis (chronic). 5) mm: mesangial matrix.

*Confounding variables:* Donor and recipient age, HLA compatibility and PRA, delayed graft function, BMI, CMV infection, concomitant treatment (statins, ACEIs/ARA, beta blockers, diuretics, and ASA), scale of treatment compliance and levels of tacrolimus or CsA.

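### The primary objective is the incidence of de novo DSA, but the primary variable is DSA presence at month 24, so as written a transient positive between randomisation and month 24 is not a primary event

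*Combined protocol and SAP*

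**What the plan says.** All references are to the combined protocol and SAP.

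- **Primary objective:** "To compare the incidence of de novo DSA in stable kidney transplant patients after withdrawal of steroids in the third month post-transplant", against continued triple therapy. No time window is given there.
- **Hypothesis:** supplies the window. De novo antibody production was to be followed "by means of the sequential measurement of DSA during the first two years post-transplant", and the study also asks about "the risk factors for the appearance of de novo DSA in these patients".
- **Secondary objectives, item 5:** "To assess the adherence to treatment with immunosuppressors in the two treatment groups and its impact on the generation of DSA", which again concerns antibodies newly formed.
- **Study design and duration:** inclusion criterion d is "Absence of de novo DSA at the time of randomization". The design is given as follows: "This was a randomized, open-label clinical trial with two treatment arms and a follow-up of two years".
- **Efficacy variables:** the primary variable "was the presence of donor-specific anti-HLA antibodies (DSA) at 24 months".
- **Monitoring of DSA:** testing before transplant and at months 3, 6, 12, 18 and 24, with MFI above 500 counted as positive.
- **Statistical analysis plan:** a repeated-measures model for DSA over time, and a regression on the generation of de novo DSA. Neither is named as the primary analysis.
- **Preliminary results, section on DSA and acute rejection:** concludes on the appearance of DSA over the first two years, without counts.

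**The concern.** Incidence counts every patient who becomes positive during a period. Presence at month 24 counts only those positive at one visit. Among patients negative at entry, the two agree only if nobody who became positive was negative again by month 24.

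The protocol itself contains one route to disagreement. Acute humoral rejection was treated with "plasmapheresis, immunoglobulins, and rituximab, either alone or in combination" (Treatment schedule, other treatments). The withdrawal criteria say that such patients were still followed for the intention-to-treat analysis. A patient whose antibodies cleared would therefore stay in that analysis as a non-event.

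At stake is what the main conclusion means. It could mean no DSA at month 24, no DSA at any visit, or some DSA without a difference between arms. The objective needs the any-visit result; the stated variable delivers the first. Uncounted cases could lie in either arm.

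**Working it through.** The documents give no sample size, assumed DSA rate or DSA count, so there is no planned figure to reproduce. The check has three steps.

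**1. Text comparison.** Take a patient negative at month 3, positive at month 12 and negative at month 24.

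| Section | Is this patient a case? |
|---|---|
| Primary objective (incidence) | Yes |
| Hypothesis (sequential measurement, appearance) | Yes |
| Efficacy variables (primary variable) | No, read literally |
| Monitoring of DSA | The positive is detected, but the MFI rule defines a positive assay, not a primary event |
| Statistical analysis plan | Data are used, but not tied to the primary variable |

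No section gives a rule for transient positivity or for a missing month-24 sample.

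**2. Bound on the treatment route.** Preliminary results give acute rejection after randomisation as 7.14% in Group A and 11.54% in Group B, without denominators. Applied to all randomised patients:

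- Group A: 0.0714 × 52 = 3.7, so at most 3 whole patients.
- Group B: 0.1154 × 53 = 6.1, so at most 6.

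The percentages also match 3/42 and 6/52 exactly, though those denominators are inferred. Humoral rejection is a subset of all rejection, so these are ceilings for cases cleared by treatment. Clearance without treatment could add cases, but no rate is given.

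**3. What a month-24 result of 0/52 versus 0/53 could hide.** This assumes zero positives at month 24 and every patient sampled at every visit; the documents state neither. The difference is d = p_B − p_A. The Newcombe limits use the Wilson limits (l, u) of each proportion:

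- lower = d − √[(p_B − l_B)² + (u_A − p_A)²]
- upper = d + √[(u_B − p_B)² + (p_A − l_A)²]

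Example, six in B and none in A: p_B = 6/53 = 11.32%, Wilson 5.29 to 22.58; p_A = 0, Wilson 0 to 6.88. Lower = 11.32 − √(6.03² + 6.88²) = 2.2. Upper = 11.32 + √(11.26² + 0²) = 22.6.

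| Transient cases, A / B | Difference, points (95% CI) | Two-sided Fisher p |
|---|---|---|
| 0 / 0 | 0.0 (-6.9 to 6.8) | 1.00 |
| 3 / 0 | -5.8 (-15.6 to 2.0) | 0.12 |
| 0 / 3 | 5.7 (-2.2 to 15.4) | 0.24 |
| 0 / 5 | 9.4 (0.7 to 20.3) | 0.057 |
| 0 / 6 | 11.3 (2.2 to 22.6) | 0.027 |
| 3 / 6 | 5.5 (-6.0 to 17.4) | 0.49 |

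At five in B the interval excludes zero while the Fisher test does not reach 0.05, so any threshold depends on the method. The last row puts both arms at their ceiling: 11.32 − 5.77 = 5.5 points, with Wilson limits for A of 1.98 to 15.64. These are possible cases, not predictions.

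**The case against.** The strongest reply is that the intent is clear. The hypothesis, the objective, the serial testing, the regression on DSA generation and the wording of the results all point to cumulative appearance over two years. On that view the primary variable is loosely worded, and *at* means *by*. This is plausible and lowers the severity. It remains an inference, because no section states it, and the two readings count different patients.

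A second reply is that no effect is shown. That stands. One natural reading of the results is that no DSA appeared, and then both definitions agree. The lack of counts in a short preliminary summary is also a reporting gap and not in itself a flaw in the endpoint.

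A third reply is that serial positives are not lost. This also stands: they are detected and analysed, but lie outside the primary variable as written.

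A reader might go further and infer that transient DSA probably changed the result. The documents do not support this. Four or more cases in Group A exceed the rejection ceiling for the treatment route. Six in Group B would need essentially every patient with rejection there to have had humoral rejection with DSA that cleared by month 24. Nor can a loss of power be stated, since that needs an incidence and a clearance rate, and neither is given.

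**Conclusion.** The mismatch is real. The objective is an incidence, the primary variable is a prevalence at one visit, and no section bridges them. Following the primary variable literally can miss incident cases, so this is more than missing detail.

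Whether it matters here is unknown. The effect ranges from nil, if no positivity was transient, to 11.3 points (2.2 to 22.6) at the one-sided extreme of the treatment route. That upper end assumes zero positives at month 24, complete sampling, rejection percentages applied to all randomised patients, and no uncounted case in Group A.

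It would be wrong to infer that the reported conclusion is mistaken or that the endpoint was switched; the text shows an ambiguity only. Severity is minor to moderate. Confidence is high for the mismatch and low for any effect on the result.

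**What to change.** 1. State whether the primary variable meant status *at* or *by* month 24, citing a record dated before the results.
2. If *by* was meant, reword it as first de novo DSA (MFI above 500) at any test after randomisation up to month 24, including any for-cause tests.
3. If *at* was meant, or no such record exists, keep month-24 presence as primary. Report beside it, labelled post hoc, the any-visit cumulative incidence by arm, with the difference and a Newcombe 95% CI. That result answers the stated objective.
4. In either case, give the numbers sampled and positive at each visit by arm, and mark positives seen once or repeatedly.
5. State how missing visits are handled. One option is Kaplan-Meier cumulative incidence to first positive; the proportion among fully sampled patients can serve as a sensitivity analysis.
6. Word the DSA conclusion in the preliminary results to match the definition used.

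The cost is a clarifying sentence, one table and a small re-analysis of samples already scheduled; how many were obtained is not stated. The downside is that a single low-MFI positive at one visit counts as an event in the any-visit result. Showing the month-24 result alongside, with the one-visit or repeat label, makes this visible.

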## **STATISTICAL ANALYSIS PLAN.**

Descriptive statistics are presented together with the various analyses. Both an intention-to-treat analysis and an analysis according to the final treatment were done. The categorical variables were analyzed using the chi-square test or Fisher's exact test, according to needs. The quantitative data were analyzed using the Student t test or the Mann-Whitney U test, according to needs. Changes over time in the DSA and lymphocyte subsets in the two study groups were analyzed using a general linear model for repeated measures, adjusting for confounding variables. Correlations between the various subsets were analyzed using Pearson correlation. The graft and patient survival curves were calculated with the Kaplan-Meier method. The rates of survival of the groups were compared with the log-rank test. Finally, a linear regression analysis was done to determine the factors associated with the generation of de novo DSA, including steroid withdrawal. The data were analyzed using SPSS 20.0.

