### **Appearance of donor-specific anti-HLA antibodies (DSA) and acute rejection.**

Steroid withdrawal at the third month post-transplant did not result in the appearance of DSA in patients with a low immunological risk, at least during the first two years of follow-up and using a MFI >500. No significant differences were found in the number of patients who experienced acute rejection after randomization between Group A (7.14%) and Group B (11.54%).

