### **Graft and patient survival.**

After randomization both graft and patient survival were 100% in the two treatment arms.

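### Biopsy-confirmed rejection has no time-to-event analysis, no stated denominator and no rule for incomplete follow-up, and the reported percentages cannot come from all randomised patients

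*Combined protocol and SAP*

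**What the plan says.** Under Efficacy variables, item b reads "Rate of acute clinical rejection, confirmed by biopsy, calculated glomerular filtration rate (determined by aMDRD) and proteinuria at 3, 6, 12 and 24 months". The months may belong to all three measures or only to filtration rate and proteinuria.

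The Statistical Analysis Plan names no method for rejection. Its general rule is "The categorical variables were analyzed using the chi-square test or Fisher's exact test, according to needs". Time-to-event methods appear only for survival: "The graft and patient survival curves were calculated with the Kaplan-Meier method", followed by "The rates of survival of the groups were compared with the log-rank test". No denominator, censoring rule or missing-outcome rule is given for rejection.

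On follow-up, the Study Design section says "The minimum follow-up period was 24 months". The withdrawal criteria say "Any participant could withdraw from the study at any time, withdrawing their consent, with no need to justify their decision", and the investigator may also withdraw patients. Those with humoral or steroid-resistant rejection are withdrawn but still followed for the intention-to-treat analysis.

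The preliminary results report acute rejection after randomisation as 7.14% (Group A) and 11.54% (Group B), described as not significantly different, without counts, denominators, p-value or confidence interval. On survival they say "After randomization both graft and patient survival were 100% in the two treatment arms".

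**The concern.** Rejection is a main clinical risk to weigh against the benefits of steroid withdrawal, and secondary objective 3 asks for immunological dysfunction to be compared between the arms. Its events can be dated, because a biopsy is required before, or within 48 hours of, starting anti-rejection treatment.

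A crude proportion estimates the 24-month risk properly only if everyone is followed to that point. If some are not, the analyst must count the leavers as rejection-free, which understates the risk, or drop the event-free leavers, which overstates it. If one arm loses more patients than the other, the error does not cancel in the comparison. The plan does not say which choice is made, and the reported percentages show that some patients were left out.

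**Working it through.** **Inputs.** Randomised: 52 in Group A, 53 in Group B (Preliminary Results). Rejection: 7.14% and 11.54%. Safety percentages and p-values: Safety assessment section. The plan states no sample size, power or dropout rate, so there is no planned figure to reproduce.

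**Step 1: do the percentages fit the randomised arms?** They do not. Counts over 52 give 3/52 = 5.77% and 4/52 = 7.69%, and nothing between. Counts over 53 give 6/53 = 11.32% and 7/53 = 13.21%. Going through every count and denominator up to the arm size:
- 7.14% fits only 1/14, 2/28 or 3/42;
- 11.54% fits only 3/26 or 6/52.

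So at least 52 − 42 = 10 Group A patients (10/52 = 19.2%) and at least 53 − 52 = 1 Group B patient (1/53 = 1.9%) are outside the rejection figures.

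**Step 2: were full arms used elsewhere?** Yes, for safety, by Fisher's exact test:
- infections, 5/52 vs 12/53: p = 0.110 (stated 0.110);
- neoplasms, 2/52 vs 1/53: p = 0.618 (stated 0.618);
- cardiovascular, 3/52 vs 2/53: p = 0.678 (stated 0.677).

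**Step 3: possible bias if the uncounted patients left early.** Assume the same true risk p in both arms over 21 months (month 3 to month 24 after transplant), constant hazards, and leaving unrelated to rejection, with proportion d = 10/52 in A and 1/53 in B. Put H = −ln(1 − p) and C = −ln(1 − d).
- Events observed over all randomised: R = H/(H + C) × [1 − exp(−(H + C))].
- Events over events plus completers: R / [R + exp(−(H + C))].

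For p = 8% in Group A: H = 0.0834, C = 0.2136, R = 0.2808 × 0.2569 = 7.21%. The second rate is 0.0721/(0.0721 + 0.7431) = 8.85%.

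| True risk, both arms | Leavers counted rejection-free: A, B | B − A | Event-free leavers dropped: A, B | B − A |
|---|---|---|---|---|
| 8% | 7.21%, 7.93% | +0.7 points | 8.85%, 8.07% | −0.8 points |
| 11.54% | 10.41%, 11.43% | +1.0 points | 12.72%, 11.64% | −1.1 points |

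The false difference is about 1 point, and its sign depends on how leavers are counted. For scale, the 95% half-width for 3/42 vs 6/52 is 1.96 × √(0.0714 × 0.9286/42 + 0.1154 × 0.8846/52) = 11.7 points.

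**Step 4: would the conclusion change?** Event and censoring times are not given, so Kaplan-Meier estimates can only be bounded. Take the largest compatible counts (3/42 and 6/52).
- No rejection among the uncounted: A lies between 3/52 = 5.8% and 3/42 = 7.1%, B between 6/53 = 11.3% and 6/52 = 11.5%. The difference is 4.2 to 5.8 points, against 4.4 reported. Fisher p is 0.49 (3/52 vs 6/53) to 0.73 (3/42 vs 6/52).
- All 10 uncounted in A rejected, the one in B did not: 13/52 = 25.0% vs 6/53 = 11.3%, p = 0.08, direction reversed.
- None in A, the one in B rejected: 3/52 vs 7/53 = 13.2%, p = 0.32.

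If the true fractions were 2/28 and 3/26, 24 and 27 patients would be uncounted. The extremes would then run from 2/52 (3.8%) to 26/52 (50.0%) in A and from 3/53 (5.7%) to 30/53 (56.6%) in B, too wide to settle anything.

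**The case against.** Follow-up is planned to be the same for everyone, at least 24 months. Patients with humoral or steroid-resistant rejection stay under observation, those who stop treatment remain in the intention-to-treat analysis, and no death or graft loss cut follow-up short. With complete follow-up, a 24-month proportion is valid. A right to withdraw does not show that patients left, still less that the arms lost different numbers. All of this stands.

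Three stronger readings are tempting, and the documents support none of them.
- *Rejection was analysed at fixed visits.* That is one reading of item b. Biopsies are taken on suspicion, the results count patients with rejection at any time after randomisation, and month 3 is the randomisation point, so it cannot be an outcome time for later rejection.
- *Unequal follow-up has distorted the comparison.* The percentages show patients left out of a denominator, not patients lost to the study. With 3/42 and 6/52 the exclusion is unequal (19.2% vs 1.9%). With 2/28 and 3/26 it is nearly balanced (24/52 = 46% vs 27/53 = 51%), and much of any bias from unrelated leaving would cancel.
- *The group labels were swapped, since 6/52 matches the size of Group A.* Nothing else in the text suggests this, and 7.14% would still not fit 53.

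Kaplan-Meier is also no full cure. It assumes that censoring is unrelated to rejection, patients with no assessment after randomisation contribute nothing, and it does not narrow the 5.8% to 25.0% range above. Finally, planning Kaplan-Meier for survival was not an error because no deaths or graft losses followed.

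**Conclusion.** The point holds as a gap in the plan: rejection has no time-to-event method, no stated denominator and no rule for incomplete follow-up. That the reported percentages omit at least 10 of 52 and 1 of 53 patients follows from arithmetic alone, provided the percentages are correctly printed. Why those patients were omitted is unknown.

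Bias is conditional. If the omitted patients left early, independently of rejection, at 19.2% and 1.9%, it is about 1 point in either direction, small beside a half-width of nearly 12 points. The non-significant result probably stands: with the largest compatible counts Fisher p is 0.49 to 0.73 if no uncounted patient rejected, and stays above 0.05 at the extremes shown. That reassurance weakens if the smaller fractions apply. Non-significance is in any case little evidence of equal risk: power for 7.14% vs 11.54% at 52 and 53 patients is about 12% (two-sided 0.05 assumed).

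This is a worthwhile, inexpensive improvement to an important safety comparison. It is not a demonstration that the reported comparison is wrong.

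**What to change.** In the Statistical Analysis Plan, add an analysis of time from randomisation to first biopsy-confirmed acute rejection in all randomised patients by assigned arm, with Kaplan-Meier and log-rank. Censor event-free patients at their last graft assessment.

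Report cumulative incidence by arm at month 24 and the difference with its 95% confidence interval. State whether month 24 runs from transplant or from randomisation: the final protocol biopsy is timed from randomisation under Efficacy variables, but from transplant in the results.

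Give counts, denominators, numbers at risk, length of follow-up and reasons for loss by arm, and explain the reduced denominators behind 7.14% and 11.54%. Keep Fisher's test as supporting. Add a sensitivity analysis for patients with unknown outcome, with best and worst cases by arm. As results are already known, label the analysis as added afterwards.

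The cost is a short addition to the plan and a re-run with methods it already names, assuming that rejection and last-assessment dates are in the database, which the documents do not state. With no deaths or graft losses after randomisation, no competing-risk method is needed. The downside is a little more analysis and reliance on censoring being unrelated to rejection, which the sensitivity analysis is there to probe.
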